1. INTRODUCTION

For all relapsed B cell derived hematologic malignancies, allogeneic bone marrow transplantation (allo BMT) is often the most definitive curative intent therapy. Historically, there have been four obstacles decreasing overall survival (OS) associated with allo BMT: preparative conditioning toxicity, donor availability, graft-versus-host-disease (GVHD) and disease relapse. Reduced intensity conditioning (RIC) regimens have dramatically reduced alloBMT toxicity and have expanded the use of this therapy to patients up to 75 years of age.(1-3) The use of alternative donors has resulted in an average of 2.7 donors for each patient in Johns Hopkins University.(4) The use of post-transplant cyclophosphamide has reduced the incidence of Grade III-IV GVHD to 6% - 11%.(5-7) However, disease relapse after successful engraftment during allo BMT remains the limiting factor for improving overall survival. (5, 6, 8)

Currently, in order to improve OS, the BMT program at JHH has recently focused on the introduction of anti-neoplastic therapy post transplantation. We use the allo HSCT as a platform to allow a new intolerant immune system to interact with a post allo HSCT biologic or therapeutic intervention. Currently, to improve overall survival, the focus of the BMT program at JHH the introduction of anti-neoplastic therapy post transplantation: where the allo BMT serves as a platform to allowing a new intolerant immune system to interact with the post allo BMT intervention. The importance of post BMT therapy has been made evident with tyrosine kinase inhibition (TKI) in Ph+ ALL and Ph+ CML, where patients who had disease progression while on TKI therapy pre-allo BMT enjoy marked improvement in OS when TKI is part of a maintenance program (9-12); the use of DNA hypomethylation agents after allo BMT for relapsed myeloid malignancies (13); or the use of rituximab after allo BMT in follicular lymphoma (PMID 26183076). At JHH we are currently, utilizing post allo BMT: TKI in Ph+ leukemia's, sorafenib and other multi-kinase inhibitors in FLT3-ITD AML, and 5-azacytidine in MDS patients.

1.1. HYPOTHESIS

Idelalisib can be safely used as maintenance therapy after allo HSCT in patients with B cell derived hematologic malignancies.

2. OBJECTIVES

2.1. PRIMARY ENDPOINT

To evaluate the safety of idelalisib, as post alloHSCT maintenance therapy in patients with B-cell hematologic malignancies, by comparing to placebo.

2.2. SECONDARY ENDPOINT

Event free survival at one year

2.3. TERTIARY ENDPOINTS

To explore the association between potential biomarkers, clinical activity and/or toxicity of Idelalisib administered after allogeneic BMT. Multi-color flow cytometric analyses of immune markers pre- and post-treatment, high-throughput DNA sequencing of rearranged TCR β CDR3 regions from T cell genomic DNA, cytokine measurements, and immunohistochemistry is planned. In addition, we may perform exploratory gene expression analysis of immune biomarkers in the bone marrow aspirates and whole or targeted exome sequencing of the lymphoma cells.

3. INCLUSION/EXCLUSION CRITERIA

3.1. INCLUSION CRITERIA

1. ≥ 18 years of age
2. Patients having undergone alloHSCT to treat a B-cell derived hematologic malignancy: accepted alloHSCT regimens include: myeloablative or reduced intensity conditioning from any donor (matched, partially mismatched or cord) and any source (peripheral blood, bone marrow, or cord).
3. T bili ≤ 1.5 mg/dL except for patients with Gilbert's syndrome or hemolysis
4. AST, ALT and alk phos all $< 2.5X$ ULN
5. Karnofsky performance score ≥ 40
6. ECOG ≤ 3
7. For women of childbearing potential, a negative serum or urine pregnancy test with sensitivity less than 50 mIU/m within 72 hours before the start of study medication.
8. Use of two forms of contraception with less than a 5% failure rate or abstinence by all transplanted patients for a minimum of 1 month after the last dose of Idelalisib. For the first 60 days post-transplant,

transplant recipients should be encouraged to use non-hormonal contraceptives due to the potential adverse effect of hormones on bone marrow engraftment.

9. Ability to receive oral medication.
10. Ability to understand and provide informed consent.

3.2. EXCLUSION CRITERIA

1. ECOG >3 (Karnofsky <40%)
2. ALT, AST >2.5 ULN or total bilirubin >1.5 ULN (not attributable to Gilbert's)
3. Women who are pregnant or breastfeeding.
4. Exclude if patient has cirrhosis or is currently being actively treated for hepatitis C.
5. History of positive HIV-1 or HIV-2 serologies or nucleic acid test.
6. Active hepatitis B infection as documented by positive Hepatitis B PCR assay
7. Use of investigational drug, other than the study medications specified by the protocol, within 30 days of transplantation.
8. Receipt of a live vaccine within 30 days of receipt of study therapy.
9. \geq Grade II aGVHD
10. The presence of any medical condition that the Investigator deems incompatible with participation in the trial
11. Subjects who are required to use a medication classified as a strong CYP3A inducer or inhibitor. An exception can be made for those patients required to take azole based antifungal prophylaxis and/or treatment.

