4. STUDY PROCEDURES

- Idelalisib, 100mg twice daily, starting day +90 (+/- 10 days) and at least five days after the discontinuation of filgrastim, if ANC greater than 1000 and PLT $50 > \text{Gi/L}$ and continued through day +270. Patients will have a CBC with platelet count and comprehensive metabolic panels performed every 14 days beginning at day +90 through day +120, then monthly through day +270.

Patients will be monitored for treatment-limiting toxicities defined as Idelalisib interruption for >14 days, or any other Grade 3 or higher adverse events as defined by CTCAE IV not captured in the protocol for dose de-escalation. All Adverse events will be collected and assessed for causality but only AEs Grade 2 and higher will be recorded on the Master AE log. Patient's idelalisib will be dose adjusted for the expected toxicities of idelalisib including pneumonitis, hepatitis, neutropenia, thrombocytopenia and loose stools.

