6. STUDY STATISTICS

This is a phase I study of Idelalisib, an orally-administered, selective inhibitor of Phosphoinositide 3 kinase (PI3K)- δ . It has been successfully used pre-transplant to induce partial and complete responses in many B-cell derived malignancies. In this study Idelalisib will be evaluated in the post-transplant setting. Patients receiving a standard of care allogeneic hematopoietic stem cell transplant from any source: cord, marrow, or peripheral blood will be eligible. Patients will be randomized in a 2:1 ratio to either 100 mg Idelalisib twice daily from day 90 (\pm 10 days) following transplant, Arm A, or a placebo, Arm B, and monitored for toxicity until day 270.

Study treatment plan: Idelalisib day +90 [+/- 10 days), 100mg twice daily, and at least 5 days after the discontinuation of filgrastim if ANC is greater than 1,000 and PLT 50>Gi/L and <grade 2 aGVHD. Patient's Idelalisib will be dose adjusted for the expected toxicities of Idelalisib including pneumonitis, hepatitis, neutropenia, thrombocytopenia and loose stools.

Primary endpoint and design: The primary goal of this study is to evaluate the safety of Idelalisib as post-transplantation maintenance in patients undergoing an allogeneic BMT. In addition to the allowed dose reductions, a safety monitoring plan will be implemented to ensure that other treatment-limiting events are not elevated. The study will be monitored between the date of randomization and day 270 post-transplant. For safety monitoring, treatment-limiting toxicities will be defined as Idelalisib interruption for >14 days, or other grade 3 or higher adverse events as defined by CTCAE IV not captured in the protocol for dose de-escalation. The trial will assume that, *a priori*, the probability of these events in both arms of the study will follow a Beta (0.10, 0.90) prior distribution. This distribution corresponds to an assumption that 10% of patients might experience a treatment-limiting toxicity.

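### Exclusion 7 ties the investigational-drug washout to transplantation, so the written criteria do not exclude use of another trial agent in the weeks just before first dose at day +80 to +100

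*Combined protocol and SAP*

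**What the plan says.** Section 3.2 of the protocol, exclusion 7, rules out "Use of investigational drug, other than the study medications specified by the protocol, within 30 days of transplantation". The next criterion, exclusion 8, rules out "Receipt of a live vaccine within 30 days of receipt of study therapy". Two adjacent lines thus use the same 30 days with different reference points.

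Transplant is already complete at entry (section 3.1, inclusion 2). Consent is taken from day +60 to day +100 (section 4.3, footnote a; section 10.2). Section 4 has study drug "starting day +90 (+/- 10 days"), and section 6 gives the same window: "Patients will be randomized in a 2:1 ratio to either 100 mg Idelalisib twice daily from day 90". On toxicity, section 6 says: "The study will be monitored between the date of randomization and day 270 post-transplant".

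Two other exclusions come near the subject. Exclusion 10 concerns "The presence of any medical condition that the Investigator deems incompatible with participation in the trial". Exclusion 11 concerns "Subjects who are required to use a medication classified as a strong CYP3A inducer or inhibitor", with an exception for azole antifungals.

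**The concern.** A washout before a trial drug normally refers to the first dose of that drug. Here it refers to an event some three months earlier. An agent taken shortly before transplant excludes a patient; one taken the day before first dose does not.

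The primary objective is safety against placebo, judged by treatment-limiting toxicity. Sections 4 and 6 define this as an interruption of more than 14 days, or another grade 3 or higher event not covered by the dose-adjustment rules. The definition sets no attribution condition. Late or continuing effects of another agent could therefore enter the primary comparison. They could also affect the GVHD incidences in section 6 and the pre-treatment immune values that serve as baseline in section 7.2.

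Such effects might be hard to identify afterwards. The attribution categories in section 9.4 are transplantation, idelalisib and other protocol-directed procedures, with none for another trial drug. The schedule of assessments has no concomitant-medication row.

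**Working it through.** The plan states no figure for this interval, so there is nothing to reproduce. The main check is a day count with transplant as day 0.

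**Inputs**
- Washout: 30 days, anchored to transplant (section 3.2, exclusion 7).
- First dose: 90 − 10 = day +80 to 90 + 10 = day +100 (sections 4 and 6).
- Earliest consent, hence earliest possible randomization: day +60 (section 4.3). The exact day of randomization is not stated.

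**Uncovered interval = day of first dose (or randomization) − last day covered by exclusion 7.** The phrase "within 30 days of transplantation" can be read in two ways.

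| Reading | Window | Before first dose | Before day +60 |
|---|---|---|---|
| (a) before transplant | day −30 to 0 | 80 − 0 = 80 to 100 − 0 = 100 days | 60 − 0 = 60 days |
| (b) either side | day −30 to +30 | 80 − 30 = 50 to 100 − 30 = 70 days | 60 − 30 = 30 days |

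Under both readings, the 30 days before first dose lie wholly outside the window.

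**What the criterion does catch.** Pre-transplant use on days −30 to 0 falls 80 + 0 = 80 to 100 + 30 = 130 days before first dose.

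**Comparison with the anchor of exclusion 8.** Purely as illustration, 30 days before first dose would be days +50 to +80 for a day +80 start, or +70 to +100 for a day +100 start. Even under reading (b), 50 − 30 = 20 to 70 − 30 = 40 days separate that period from the current window.

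**Does another section close the gap?**
- Exclusion 10 covers medical conditions, not other trial drugs.
- Exclusion 11 and Appendix 4 cover CYP3A and PgP interactions, not investigational drugs as a class.
- Section 4.1 does not list starting another trial agent as a reason to stop study therapy.

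None of them does.

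**Sensitivity of the stopping rule to one event.** This shows how much a single misassigned event can weigh; it does not estimate how often one would occur. Section 6 uses Beta(0.10, 0.90) priors and calls for a safety review if P(Arm A rate − Arm B rate > 0.10) is at least 75%. With x events in n patients the posterior is Beta(0.10 + x, 0.90 + n − x). At the first look, with 10 patients on Arm A and 5 on Arm B under 2:1 allocation:

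| Arm A | Arm B | Posteriors (A; B) | Probability | Review? |
|---|---|---|---|---|
| 3/10 | 0/5 | Beta(3.1, 7.9); Beta(0.1, 5.9) | 0.90 | yes |
| 3/10 | 1/5 | Beta(3.1, 7.9); Beta(1.1, 4.9) | 0.52 | no |
| 2/10 | 0/5 | Beta(2.1, 8.9); Beta(0.1, 5.9) | 0.71 | no |

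Starting from the first row, one more control event, or one fewer Arm A event, takes the result below the cutoff.

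**The case against.** The best defence is the design. Allocation is randomized and double-blind, so exposure before randomization cannot depend on the assigned arm. It is balanced in expectation and acts mainly as noise, in a trial that already admits any donor, graft source and conditioning. This stands: no directional bias is shown. Chance imbalance remains possible with 30 and 15 patients.

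The entry and start conditions also limit carry-over toxicity. They include limits on bilirubin and transaminases, no aGVHD of grade II or higher, minimum neutrophil and platelet counts, and at least five days off filgrastim. Adverse events are collected from first dose (section 9.3.1). These conditions narrow the consequence, but they would not catch delayed effects or an agent still being taken.

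Three stronger readings are tempting, and the documents do not support them:
- **That the protocol permits other trial agents up to randomization.** It is silent. The supportable statement is that the written criteria do not exclude such patients; investigators might still screen them out informally.
- **That treatment-limiting toxicity counts events whatever their cause.** The definition states no attribution condition, but section 4 has adverse events assessed for causality, and section 5.1 describes the stopping trigger in terms of toxicity caused by idelalisib or placebo. Attribution is unspecified.
- **That the flaw is worth 6.7 percentage points on the control rate.** The figure 1/15 = 6.7% is the weight of any one placebo event from any cause. The stopping-rule table above has the same limit.

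**Conclusion.** The point holds as a minor one: the criterion is stated, but its reference point leaves the weeks immediately before first dose uncovered. The gap is 80 to 100 days under reading (a) and 50 to 70 days under reading (b). The conclusion does not depend on which reading is meant, nor on the day of randomization within day +60 to +100.

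The effect on the toxicity comparison cannot be computed. It depends on how many patients take another trial agent between transplant and first dose, and the documents give no rate. Section 1 describes a program focused on anti-neoplastic therapy after transplant, which makes such exposure plausible, but it does not call those agents investigational. What can be said is that the comparison is small enough for one event to matter at the first look, and that randomization protects it only on average.

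**What to change.** Anchor exclusion 7 to the start of study therapy, as exclusion 8 does. If the transplant anchor also serves a purpose, keep it as a second condition and say whether it means before transplant or either side. State separately whether other investigational agents are allowed during study therapy. The sponsor should choose the washout length; the 30 days in exclusion 8 were set for live vaccines and need not carry over.

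The cost is one revised eligibility line and one added sentence. A small number of otherwise eligible patients may be excluded; the documents do not allow that number to be estimated.

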3.3. ENROLLMENT

Approximately 60 patients who have undergone allo BMT for B-cell derived hematologic malignancies.

4. STUDY PROCEDURES

- Idelalisib, 100mg twice daily, starting day +90 (+/- 10 days) and at least five days after the discontinuation of filgrastim, if ANC greater than 1000 and PLT $50 > \text{Gi/L}$ and continued through day +270. Patients will have a CBC with platelet count and comprehensive metabolic panels performed every 14 days beginning at day +90 through day +120, then monthly through day +270.

Patients will be monitored for treatment-limiting toxicities defined as Idelalisib interruption for >14 days, or any other Grade 3 or higher adverse events as defined by CTCAE IV not captured in the protocol for dose de-escalation. All Adverse events will be collected and assessed for causality but only AEs Grade 2 and higher will be recorded on the Master AE log. Patient's idelalisib will be dose adjusted for the expected toxicities of idelalisib including pneumonitis, hepatitis, neutropenia, thrombocytopenia and loose stools.

4.1. PREMATURE DISCONTINUATION OF STUDY THERAPY

Study therapy is defined as initiation of any study-mandated therapies and study procedures described in [section 4.0](#).

Study therapy will be discontinued for the following reasons:

- Adverse experience. If a participant suffers from an adverse experience that, in the judgment of the Principal Investigator, may present an unacceptable consequence or risk to the participant.
- Intercurrent illness or infection. If during the course of the study a participant develops an illness or infection that is not associated with the condition under study and that requires treatment not consistent with protocol requirements; or, if a participant develops an intercurrent illness that in the judgment of the Principal Investigator justifies discontinuation.
- Protocol violation. If a participant cannot comply with the study protocol and the protocol deviations are sufficient to jeopardize his or her well-being or the integrity of the study.
- Pregnancy.
- Investigator discretion. If the Investigator determines that the study therapy is no longer in the best interests of the participant.
- If the participant is unwilling or unable to continue on study therapy.

4.2. PREMATURE TERMINATION OF A PARTICIPANT FROM THE STUDY

Participants will be prematurely terminated from the study for the following reasons:

- **Withdrawal of consent.** If for any reason a participant withdraws consent during the study they will be terminated from the study. All information and biospecimens collected from the participant prior to their withdrawal of consent will continue to be utilized by the study.
- **Failure to return.** Participants who do not return for visits and who do not respond to repeated attempts by the site staff to have them return will be considered *lost to follow-up*.

4.3. TABLE 1. SCHEDULE OF ASSESSMENTS

	Screening and Baseline ()	Cycle 1, Day 1 Day +90 (± 10 Days)) Cycle 1, Day 15	(± 7 Days) Cycles 2-6, Day 1	30 days Post last dose	Month 12 (± 14 Days)
Informed Consent ^a	Days 60 -100					
Medical History	X					
Physical Exam	X	X		X	X	X
AE Assessment	X	X		X	X	X
CBC with diff	X	X	X	X	X	X
Comprehensive metabolic panel e (CMP) ^b	X ^b	X ^b	X ^b	X ^b	X ^b	X ^b
PT, PTT, INR	X					
Serum β -HCG (if applicable)	X					
CMV PCR ^d	X ^d	X	X	X		
Dispense Idelalisib		X		X		
Standard of care per institution						
T-cell chimerism	X					X
Bone marrow biopsy (as std of care)	X					X
aGVHD/cGVHD assessments	X	X	X	X		X
Correlative studies ^c	X	X		X ^c		X

^aInformed consent will be collected beginning on Day +60 after BMT until Day +100.

^b CMP to include BUN, creatinine, sodium, potassium, chloride, AST, ALT, total bilirubin, alkaline phosphatase.

^c Additionally specimens should be obtained from peripheral blood and bone marrow collections as a part of routine clinical care such as GVHD, toxicity and/or disease relapse Correlative peripheral blood samples should be collected on Day 1 of every other cycle beginning with Cycle 2

^d Cytomegalovirus (CMV) viral load assay will be monitored by PCR every 14 days between days +90-and day +120, then monthly through day +270: treat according to BMT policy guidelines.

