5. KNOWN TOXICITIES AND DOSE ADJUSTMENTS

5.1. KNOWN TOXICITIES OF IDELALISIB

Idelalisib is FDA approved for the treatment of relapsed chronic lymphocytic leukemia/small lymphocytic lymphoma and follicular B-cell non-Hodgkin lymphoma. Idelalisib may cause:

- ALT/AST elevations and hyperbilirubinemia (most frequently occurs within the first 12 weeks of treatment); incidence of serious hepatotoxicity: 14.0%
- Diarrhea (mean time to occurrence 7.2 months); incidence of serious/severe diarrhea: 14.0%
- Pneumonitis; incidence <5%
- Neutropenia: Grade 3 or 4 neutropenia occurs in approximately 31% of patients receiving the 150mg bid dose.
- Rash: Grade 3 or 4 rash occurred in approximately 21% of patients receiving the 150mg BID dose.
 - CYP3A affects: CYP3A inducers can reduce the AUC of idelalisib by 75%; CYP3A inhibitors can increase the AUC of idelalisib by 1.8 fold; idelalisib is strong CYP3A inhibitor. A list of these drugs can be found in appendix 4. Importantly, with direct relevance to this study is the lack of data supporting strong interaction with voriconazole. Azoles are often the medication of choice for patients with suspect fungal or anti-bacterial non-responsive fevers during alloBMT. The elimination of idelalisib is predominantly mediated by the hepatic pathway. Idelalisib is primarily metabolized by aldehyde oxidase with a lesser involvement of cytochrome P450. The major metabolite of idelalisib is GS-563117. Data indicate that CYP3A inhibition by concurrent use of azoles may result in modestly higher exposures of idelalisib, but the change is not of clinical relevance²¹. In this study, as the dosing of idelalisib is already reduced to 100mg bid to provide additional risk mitigation. Additionally, patient's receiving azole therapy while on idelalisib will have serum levels monitored to adjust to target levels.

Therefore, to protect patients in this study the following measures are employed:

- Patients will have comprehensive metabolic panels performed every 2 weeks through day +120, then monthly through day +270.
- Patients post alloBMT may develop intestinal aGVHD which may present with diarrhea or ileus. All patients with ≥ 3 grade diarrhea will also be evaluated for aGVHD in addition to idelalisib dose modification.
- Patients post alloBMT may develop aGVHD which often presents with a generalized cutaneous rash. All patients with ≥ 3 grade rash will also be evaluated for aGVHD in addition to potential idelalisib dose modification.

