Transaminitis and hyperbilirubinemia can occur with idelalisib use and are also common in allogeneic bone marrow transplant recipients. For patients experiencing an AST/ALT or bilirubin >5x ULN that is unexplained by other factors, hold study drug until the parameter is \leq 2ULN and restart at 100mg once daily. If the parameter should rise again >5 ULN, discontinue study drug. For AST/ALT >20x ULN (or Bilirubin >10x ULN), regardless of attribution, study drug should be permanently stopped.

DIARRHEA

Diarrhea can occur with idelalisib use and is also common in allogeneic bone marrow transplant recipients. Prior to major pharmacologic intervention, common infectious causes of loose stooling should be evaluated. For loose stools, in the absence of major infections, anti-motility agents may be offered and/or light steroid preparations. For patients with significant stooling, >1L daily, hold study drug and consider colonic biopsy if there is evidence to suggest aGVHD. Once stooling is <0.5L day, restart at 100mg oncedaily. If stooling should

again increase to >1L daily, discontinue study drug. For life-threatening diarrhea, study drug should be permanently stopped.

NEUTROPENIA AND THROMBOCYTOPENIA

Neutropenia and thrombocytopenia can occur with idelalisib use and are also common in allogeneic bone marrow transplant recipients. For ANC < 500 or PLT < 25,000, monitor CBC with differential weekly, hold study drug until ANC >1,000 and PLT count >50,000 and restart at the original dose. If a subject develops ANC < 500 or PLT < 25,000 a second time, hold study drug until ANC >1,000 and PLT count >50,000 and restart at 100mg once daily. If a subject who is on 100mg once daily develops ANC < 500 or PLT < 25,000, discontinue study drug.

Acute GVHD: Patients with symptomatic aGVHD will be treated as per institutional guidelines. If after seven days of therapy there is evidence of progressive aGVHD, study drug will be stopped for at least seven days. If it is determined that study drug was not causative of the aGVHD it may be restarted at the discretion of the primary oncologist. If after 14 days of active therapy there is no improvement of the aGVHD, study drug will be stopped for at least seven days. If it is determined that study drug was not causative of the aGVHD persistence it may be restarted at the discretion of the primary oncologist.

LATE ONSET NEUTROPENIA (LON)

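### Scheduled GVHD and adverse-event visits follow time on drug, so patients who stop early lose active assessment before day 270

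*Combined protocol and SAP*

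**What the plan says.** **Calendars.** Section 4.3 and Appendix 2 carry the same visits: screening, Cycle 1 Day 1 (day +90), Cycle 1 Day 15, "Cycles 2-6, Day 1", "30 days Post last dose" and Month 12. The row "aGVHD/cGVHD assessments" is marked at every visit through Cycles 2-6, blank at the post-dose visit, and marked again at Month 12. The AE row is marked at Cycles 2-6, the post-dose visit and Month 12.

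**Stopping drug and leaving the study.** Section 4.1 opens its list with "Study therapy will be discontinued for the following reasons". Section 4.2 lists only withdrawn consent and failure to return as reasons for leaving the study. Stopping drug is therefore not leaving. However, Section 4.1 defines study therapy so that it takes in study procedures as well as treatment.

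**AE collection.** Section 9.3.2 collects grade 3 or higher AEs, and all grade III-IV aGVHD, until the participant completes or leaves the study.

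**Laboratory tests.** Section 4 sets CBC and metabolic panels by transplant day: "performed every 14 days beginning at day +90 through day +120, then monthly through day +270". Section 5.1 does the same for the metabolic panel: "Patients will have comprehensive metabolic panels performed every 2 weeks through day +120, then monthly through day +270". Footnote d of the calendar puts CMV PCR on the same clock.

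**What is reported.** Section 6 states: "The study will be monitored between the date of randomization and day 270 post-transplant". Its analysis plan gives toxicity by grade and type, cumulative incidence of aGVHD, relapse and NRM, and one-year event-free survival.

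**The concern.** The monitoring window is fixed by transplant day, but the visits that would detect GVHD and AEs within it are fixed by dosing. Followed as printed, the calendar makes the length of active assessment depend on how long a patient stays on drug.

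Stopping is not random. Section 5.2 holds or ends drug for pneumonitis, hepatotoxicity, diarrhea and cytopenias, and holds it for aGVHD that progresses or fails to improve: "If after 14 days of active therapy there is no improvement of the aGVHD, study drug will be stopped for at least seven days". Those who lose scheduled assessment are therefore the patients who have already had trouble. If more of them are on idelalisib, Arm A is observed less closely per patient than Arm B, and the difference in reported toxicity and aGVHD shrinks or reverses for reasons unrelated to the drug's safety. Sections 5.1 and 8.2 also contemplate stopping the trial on between-arm differences in toxicity, and Section 5.1 names GVHD, so this ascertainment feeds safety decisions as well as the final tables.

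**Working it through.** The plan prints no figure for assessment after stopping drug, so the check is visit-date arithmetic on the calendar.

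**Inputs.**
- Start at day +90, six cycles, end at day +270 (Sections 4 and 4.3).
- Cycle length is not stated. I assume 30 days, since (270 − 90)/6 = 30, and repeat with 28.
- Month 12 is taken as day +365 (assumption).
- With 30-day cycles, Day 1 of Cycles 1-6 falls on days 90, 120, 150, 180, 210 and 240. Cycle 1 Day 15 is day 104.

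**Formulas.**
- GVHD gap = 365 − last GVHD visit on or before the stop day.
- AE gap = 365 − (stop day + 30).
- Excess = gap − completer's gap.

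| Stop day | Last GVHD visit | GVHD gap | Excess | Post-dose visit | AE gap | Excess |
|---|---|---|---|---|---|---|
| +105 | 104 | 261 | 136 | 135 | 230 | 165 |
| +120 | 120 | 245 | 120 | 150 | 215 | 150 |
| +180 | 180 | 185 | 60 | 210 | 155 | 90 |
| +270 (completer) | 240 | 125 | – | 300 | 65 | – |

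With 28-day cycles the GVHD gaps are 261, 247, 191 and 135 days, and the AE gaps do not change.

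A stop at day +120 loses the four GVHD assessments of Cycles 3-6 (days 150 to 240), all before day 270. For AEs, the post-dose visit at day 150 stands in for Cycle 3. The 270 − 150 = 120 days that follow, to the end of the monitoring window, have no scheduled AE visit.

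**Laboratory tests.** Read from the calendar, a stop at day +120 leaves no CBC or metabolic panel after day 150. Read from Sections 4 and 5.1, both continue monthly to day +270 with no condition on dosing, leaving 365 − 270 = 95 days to Month 12. The two sources conflict, and no loss before day 270 is established.

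**Illustration (all inputs assumed).** The ceiling on missed events in Arm A is 30 × share stopping early × risk of a later GVHD event:
- 10% and 10%: 30 × 0.10 × 0.10 = 0.3 patients (1 percentage point).
- 40% and 30%: 30 × 0.40 × 0.30 = 3.6 patients (12 points).

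This is reached only if neither routine care nor AE reporting picks up any of them.

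For the comparison, suppose a true later aGVHD risk of 20% in both arms, with 30% of Arm A and 10% of Arm B stopping at day +120:
- Half of off-schedule events captured: Arm A 0.7 × 20% + 0.3 × 20% × 0.5 = 17%; Arm B 0.9 × 20% + 0.1 × 20% × 0.5 = 19%.
- None captured: 14% and 18%.
- All captured: no bias.

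**The case against.** The strongest reply is that most outcomes remain covered after drug stops.

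- **AE collection continues.** A reader might infer that early stoppers drop out of AE follow-up, or that worsening to grade III-IV aGVHD goes uncounted. The documents do not support this: Sections 4.2 and 9.3.2 keep these patients in the study and collect exactly those events. That stands. Collection without a visit, however, relies on unscheduled contact or recall at Month 12. Section 9.3.2 names only grade III-IV aGVHD, while the incidence analysis in Section 6 has no grade restriction.
- **Laboratory monitoring.** A reader might infer a long loss of liver and blood-count monitoring. The day-based text contradicts that through day +270, so only the conflict with the calendar stands.
- **One-year event-free survival.** A reader might infer bias here too. None is shown: marrow biopsy and chimerism are scheduled only at screening and Month 12 for everyone, so stopping drug removes neither.
- **Month 12 catches up.** It carries AE and GVHD assessments for all who remain, and Appendix 1 asks for the highest organ stage in the period. This makes zero capture unlikely but does not restore onset dates.
- **aGVHD stoppers already count.** The Section 5.2 rule quoted above is a hold with possible restart, and those patients already have an aGVHD event. This is fair for first onset. It does not help patients who stop for other toxicities.
- **Cycle columns could be calendar visits.** Dispensing is a separate row, so a site could skip it and keep the visit. No text says so, and the Section 4.1 definition of study therapy points the other way.

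**Conclusion.** The point holds for scheduled GVHD and AE visits. A stop at day +120 adds about 120 days without a scheduled GVHD assessment and 150 without a scheduled AE visit, compared with a completer. This assumes 30-day cycles, Month 12 at day +365, and a site that follows the calendar as printed.

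The outcomes exposed are lower-grade aGVHD, lower-grade AEs and onset dates, and hence the aGVHD incidence and the toxicity summaries. The direction of any bias, towards idelalisib looking safer, rests on more stopping in Arm A. That is a reasonable inference from the toxicities listed in Section 5.1, but the documents give no discontinuation rate. The size depends on how much routine care captures: in the comparison above, 0 to 4 percentage points.

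The treatment-limiting endpoint is largely protected, because more than 14 days off drug is itself an event.

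**What to change.** 1. In Section 4.3 and Appendix 2, label the Cycle 2-6 assessment columns by study day.
2. State that every randomised patient who has not withdrawn consent keeps the AE and GVHD assessments at those days through day +270, on or off drug, and that only dispensing stops.
3. Keep the post-last-dose visit as an additional visit and add a GVHD assessment to it.
4. Reconcile the calendars, and the Section 4.1 definition of study therapy, with the day-based laboratory text, so that it is clear which tests continue after drug is stopped.

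The cost is a change of wording plus a few extra clinic assessments in early stoppers, who are in post-transplant follow-up. For a stop at day +120 this means four GVHD assessments at the cycle-equivalent days and one at the post-dose visit, which falls on the first of those days. No patients are added.
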